7.2.2 Expedited Reporting of Serious Adverse Drug Experiences

No serious adverse events (SAE) are expected as the intervention(s) are standard in clinical practice and non-invasive. Nevertheless, study coordinator/PI will be informed of a SAE via a telephone call and preliminary information will be obtained. If all information is not known at the time of initial reporting, an initial report will still be made. The PI is responsible for following up on completion of the SAE Form. The PI will submit substantiating data in hard copy form, such as diagnostic test reports and progress notes, as requested.

During the initial telephone call, the study coordinator /PI will require the following information about the patient and the reported SAE:

1. Patient identification including participant identification number, initials, and date of birth;
2. Date of onset of the event;
3. Date of resolution of the event (or confirmation ongoing);
4. Severity of the event;

5. Assessment of the attributability of the event to study participation;
6. Whether the event is expected;
7. Action taken in treating the event and (including concomitant medications or therapies administered, whether hospitalization or prolongation of hospitalization was required, diagnostic procedures performed, and whether the patient was discontinued from the study);
8. All concomitant medications (including doses, routes, regimens, and indications);
9. Pertinent laboratory data;
10. Medical history (including time on study prior to adverse experience).

The PI will review each SAE report and evaluate the relationship of the adverse experience to underlying disease. Based on the PI's assessment of the adverse experience, a decision will be made concerning the need for further action. The primary consideration governing further action will be whether findings affect the safety of patient(s) participating in the clinical trial.

Further action that may be required includes the following:

1. Alteration of existing research by modification of the protocol;
2. Discontinuation or suspension of the study;
3. Alteration of the informed consent process by modification of the existing consent form and informing current study participants of new findings;
2. Modification of previously identified expected adverse experiences to include adverse experiences newly identified as study-related.

PI will promptly report all SAE to the I.R.B.

7.3 Withdrawal from Study Treatment Due to Adverse Experience

Patients withdrawn from receiving additional study drug due to an AE will be followed by the PI until resolution or stabilization of the event. Additional reports will be provided to the regulatory authorities when requested. Every effort will be made to follow the patient for the full study period as per the schedule of study visits.

8. Final Outcomes Assessment:

Table. Outcomes and covariates
Outcomes
Specific Aim 1. Between Group Comparisons (African Americans vs. Other): Measure change from pre-treatment to 3 months after AUTOPAP treatment: (a) Primary - average 24-hour systolic and diastolic BP (b) Secondary - central aortic blood pressure ii. average of 24-hour mean BP = diastolic + 1/3x (systolic - diastolic) iii. 24-hour urine norepinephrine & normetanephrine iv. Overnight urine 8-isoprostane levels
Specific Aim 2. (change from pre-treatment to 3 months after AUTOPAP treatment): (a) Primary (between-group comparison) - change in number of PVT lapses (b) Secondary (within-group comparisons) - i. Association of change in PVT lapses with primary outcome of specific aim 1. ii. Association of change in PVT lapses with secondary outcomes of specific aim 1. iii. Association of change in ESS scores with outcomes of specific aim 1.
Exploratory Aim 3. i. Within-group analysis of change in specific aim 1. primary and secondary outcomes (i. and ii.) with addition of Individual Ancestry as a covariate. ii. Velocity Vector Imaging (VVI) from echocardiography correlation with AHI. iii. Generate effect size estimates for AUTOPAP treatment on VVI.
Covariates: Specific Aims 1 and 2
Socio-demographic Characteristics 
 • Age (continuous) • Daily sleep duration on actigraphy (continuous) • Gender (categorical, 2 levels) • Education (categorical, 2 levels; ≤ high school, > high school) • Income per annum (categorical, 5 levels; <30K, 30-50K, 51-75K, 76-100K, >100K) • Smoking status (pack-years; continuous) • Alcohol use (number of drinks/week; continuous)
OSA Disease Severity 
 • AHI • Time below 90% oxygen saturation (T<90)
Co-morbid Medical Conditions 
 • Obesity: Body Mass Index (BMI) • General Health Status: Charlson Comorbidity Index (CCI)
Treatment Related Measures 
 • Antihypertensive drugs: Adherence and Regimen Medication Possession Ratio (MPR) and Defined Daily Dose (DDD) • Adherence to AUTOPAP: Objective device download data at 90 days

9. DATA ANALYSIS

9.1 Case Report Forms

All data required by the study protocol will be entered onto CRFs. Only authorized research personnel will enter data on the CRFs. All entries must be legible and made using indelible

black ink. If an entry error is made, a single line will be placed through the incorrect entry. The correct entry will then be made, with the correction dated and initialed by the person making the entry. Any corrections to data entered into the CRF must be made in such a way that the original entry is not obscured.

CRFs must be completed for every patient who signs an informed consent and has screening procedures performed. The CRFs will be signed and dated by the study coordinator/PI. The original completed CRFs should be kept in a locked study file and handled in accordance with JBVAMC R&D policies.

9.2 Data Quality Assurance

CRFs will be checked for correctness against source document. Once the CRF page is complete, it will be delivered to data management personnel for entry into an electronic database. Prior to data entry, the completed CRF will again be reviewed for completeness, consistency and legibility. Any discrepancies will be noted on a data clarification form (DCF). The discrepancy will be clarified on the DCF and placed in patients research record.

9.3 Data Management

PI will check data for quality control, weekly for the first month, and then biweekly. Electronic data (Microsoft office Excel) will be stored on a password-protected computer in a locked office and hard copies of data will be stored in a locked file cabinet in a locked office (PI's office, JBVAMC, Damen pavilion, Room 8508). Identifying information (MASTER LIST) will be stored separately in a designated locked cabinet at aforementioned location. Data will be backed up regularly on VA network (vhachsprasab2). Only the study coordinator/PI will have access to the keys for this cabinet. For analysis, data will be stripped of all individual identifiers and exported from Excel to the Statistical Analysis System (SAS Institute, 2011, version 9.3 or later), where appropriate labels and formats will be applied. The de-identified SAS dataset will be provided to UIC Design and Analysis Core, Center for Clinical and Translational Science for statistical analysis on VA encrypted flash drive. All scripts for statistical analysis will be documented with file headers and embedded comments; all data and analysis files will be preserved securely per JBVAMC R&D regulations. Prior to beginning analysis, descriptive statistics will be prepared for all variables and collected in a codebook. Any "wild" data values discovered will be resolved. After data analysis is complete, the electronic data will be returned to PI on the VA encrypted flash drive and no copied data will be retained on non-VA computer. If key authorized personnel leave the study/VA employment their access to research data/locked file/computers will be terminated immediately. PI will report incidents, i.e. theft or loss of data or storage media, unauthorized access of sensitive data or storage devices or non-compliance with security controls to JBVAMC R&D office/other regulatory authorities in accordance with VA policy.

9.4 Statistical Analyses

9.4.1 Power and Sample Size Estimation: The primary goal of this initial study is to estimate differences in the effect size of AUTOPAP treatment on ABP and CABP in AA and EA's with moderate to severe OSA. Our preliminary data shows a reduction in office BP 3 months after AUTOPAP treatment and the effect size difference between-groups (by ethnicity; using differences in mean \pm SD change of BP and t-tests in PASS program, <http://www.ncss.com/pass.html>) was 0.42 for systolic and 0.53 for diastolic blood pressure. We determined that 99 patients in each group (total n = 198) will provide power of 0.8 in two-tailed tests with an alpha of 0.05 to observe a difference in effect size between groups of 0.4. Based on our prior experience we anticipate an attrition rate of 10-20%. Therefore, a total of 220 (198/0.90) patients enrolled will achieve the target of 198 patients completing the study. Our preliminary study of PM in our clinical population (selected with a positive BSQ) shows approximately 95% sensitivity and specificity of PM determined AHI of ≥ 15 /hour in terms of predicting PSG-determined AHI of ≥ 15 /hour (inclusion criteria). Therefore, we expect to screen approximately 260 patients (220/0.95).

9.4.2 Data analysis: A p-value < 0.05 will be considered significant. All variables and analysis goals are listed in table above. **Specific Aim 1.** Within group changes in primary and secondary outcomes will be assessed with repeated measures ANOVA implemented with PROC MIXED in SAS. A two-sample t-test (PROC TTEST in SAS) will be used to examine between-group differences in the treatment-related changes in primary and secondary outcomes. **Specific Aim 2.** Primary outcome will be assessed with a two-sample t-test (PROC TTEST in SAS). Secondary outcomes will be assessed with partial correlations implemented with PROC CORR in SAS.

Exploratory Aims 3. Effect of Individual Ancestry on changes in primary and secondary outcomes of specific aim 1 within group will be assessed with ANCOVA implemented with PROC GLM in SAS. Correlations (of VVI with AHI and change in VVI with change in AHI) will be assessed within groups.

Residuals and outliers: Linear models require residuals from model fits to follow a normal distribution and be free of outliers. We will examine residual distributions and apply transformations to outcomes and explanatory variables as warranted to achieve normality. Further model checks will employ partial regression plots; outliers will be dealt through case removal, influence down-weighting (robust M-estimation), or bootstrapping of estimators. Missing data: We will examine patterns of missingness with respect to covariates and include any covariates differentially associated with missing data. Correctly specified linear mixed models yield unbiased estimates for data missing at random (MAR); multiple imputation can also be employed. It is possible that subjects' treatment experiences will affect missingness (dropout), in which case data is not missing at random (NMAR) or nonignorable, and requires additional modeling, such as pattern-mixture models.

Moderators: Whether a moderator variable Z affects the association of explanatory variable X and outcome Y will be examined by introducing Z and the $Z*X$ interaction in the linear model. When Z is a (0,1)-indicator variable (e.g., gender), the coefficient for Z is the adjustment to the intercept and the coefficient for $Z*X$ is the adjustment to the slope appropriate for the group coded 1; the latter coefficient tests the moderator effect.

Mediators: None hypothesized.

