Objectives:	
Primary Objectives:
 
 1. To assess the efficacy of –autoadjusting positive airway pressure (AUTOPAP) treatment in reducing 24-hour ambulatory blood pressure (ABP) in African American (AA) vs. - other (race) veterans with newly-diagnosed obstructive sleep apnea (OSA); 2. To assess the efficacy of –autoadjusting positive airway pressure (AUTOPAP) treatment in reducing central aortic blood pressure (CABP) in AA vs. other (race) veterans with newly-diagnosed obstructive sleep apnea (OSA); 3. To assess the efficacy of –autoadjusting positive airway pressure (AUTOPAP) treatment in reducing urinary biomarkers implicated in the pathogenesis of hypertension in OSA: 1) sympathetic nervous system activity (SNA; 24-hour urinary catecholamines) and 2) oxidative stress (overnight urinary 8-isoprostane) in AA vs. other (race) veterans with newly-diagnosed obstructive sleep apnea (OSA). 4. To test daytime dysfunction (excessive daytime sleepiness; EDS) as a moderator of reduction in ABP and CABP in AA and other (race) veterans following 3 months of AUTOPAP treatment. EDS will be measured objectively with psychomotor vigilance task (PVT) and subjectively with Epworth sleepiness scale (ESS). 
Secondary Objectives:
 
 5. To examine the association of reduction in ABP and CABP with genetic ancestry (using ancestry informative markers; AIMs in DNA), as genetic admixture is expected among self-identified ethnic groups (i.e., AA and other (race) veterans). 6. To analyze abnormalities in myocardial mechanics on transthoracic echocardiography (TTE) in obstructive sleep apnea and its reversibility with AUTOPAP treatment. 
Ancillary Objective:
 
 7. Tissue banking (whole blood processed for DNA, RNA, serum, and plasma) for future genomic studies.

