---	---

	will be given instructions regarding follow-up care for OSA with sleep medicine or primary care provider.
Duration of Patient Participation:	Visits 1- 3 over 7-10 days Visits 4-5 over 90-100 days
Study Duration:	Total duration: 100-110 days (4 months)
Number of Patients to initiate AUTOPAP Treatment:	220 Our sample calculations and current dropout rate 2/16 (12.5%, lower than the anticipated 20%) suggest n = 220 will provide 80% power to detect between group difference at two-sided alpha of 0.05.
Eligibility Criteria:	
Inclusion Criteria:
 
 1. Self-identified African American and Other Veterans 2. Age: 18-70 years 3. Hypertension 4. Apnea hypopnea index (AHI) ≥ 15/hour on portable monitoring (PM) 
RATIONALE ** We have modified inclusion criteria from self-identified African American and European American Veterans to African American and “Other” for the following reasons:
 
 • Our primary goal is to identify treatment response in AA compared to other race (Hypothesis: response of hypertension to AUTOPAP treatment will be higher in AA than other groups). • To improve recruitment for this study and meet target enrollment (n = 220) over next two years. 
Exclusion criteria:
 
 1. Past/current treatment of OSA or other primary sleep disorders 2. Active uncontrolled medical or psychiatric conditions 3. Shift work in preceding 6 months 4. Current illegal drug or daily alcohol use 5. Pregnancy
Treatment Effectiveness Endpoints:	
 1. Change in 24-hour ABP measures from baseline to after 3 months of AUTOPAP treatment. 2. Change in CABP measures from baseline to after 3 months of AUTOPAP treatment. 3. Change in 24-hour urinary catecholamine’s and 8-isoprostane measures from baseline to after 3 months of AUTOPAP treatment. 4. RATIONALE ** We have changed CPAP to AUTOPAP treatment as this treatment can be instituted after PM testing and eliminates the need for polysomnography guided CPAP titration. Moreover, AUTOPAP has been shown to equivalent in efficacy to CPAP in terms of symptom resolution and systemic blood pressure response.
Sleepiness as Moderators of Effectiveness:	
 5. Test association of baseline ESS and PVT with effectiveness endpoints 1 to 3. 6. Test association of change in ESS and PVT from baseline to visit 5 with effectiveness endpoints 1 to 3.

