2. STUDY OBJECTIVES

2.1 Primary Objectives

The primary goal of this study is to quantify and compare change in blood pressure (ABP and CABP) following 3 months of AUTOPAP treatment in Veterans with hypertension and newly-diagnosed OSA. We will examine changes in ABP and CABP in the context of key biomarkers implicated in the pathogenesis of hypertension in OSA: 1) sympathetic nervous system activity (SNA; 24-hour urinary catecholamines) and 2) cumulative oxidative stress (overnight urinary 8-isoprostane). ABP, CABP, and the biomarkers will be measured pre-treatment and after 3 months of AUTOPAP treatment.

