2.2 Secondary Objectives

Studies in EA suggest the presence of excessive daytime sleepiness (EDS; symptom of OSA) is associated with a more robust hypertension response to AUTOPAP treatment. Our preliminary data indicate a higher prevalence of objective EDS in AA with OSA compared to EA after adjusting for socio-demographic factors. Thus, we will examine EDS as a moderator of hypertension response to AUTOPAP treatment and identify EDS by the Psychomotor Vigilance Test; PVT (higher number of lapses per trial is objective EDS) and ESS questionnaire.

There is significant genetic admixture among self-identified ethnic groups which introduces biological heterogeneity and potential confounding. We will identify genetic ancestry by known and specific DNA sequence variation(s), called Ancestry Informative Markers (AIMs) and explore the role of genetic (i.e. biologic) ancestry as a moderator of ABP and CABP outcomes.

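### Power of 80% with 220 enrolled holds only at 10% attrition and for one endpoint at a time; no success rule covers the two primary blood pressures, and 260 to screen does not follow from 220/0.95

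*Combined protocol and SAP*

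**What the plan says.** **Sample size.** Section 9.4.1 takes 99 completers per group (198 in all) for 80% power at two-sided 0.05 and a between-group difference of 0.40 standard deviations. On attrition it says: "Based on our prior experience we anticipate an attrition rate of 10-20%. Therefore, a total of 220 (198/0.90) patients enrolled will achieve the target". The pilot effect from office blood pressure "was 0.42 for systolic and 0.53 for diastolic blood pressure". The synopsis (number of patients) refers to the sample size calculation and says that the "current dropout rate 2/16 (12.5%, lower than the anticipated 20%) suggest n = 220 will provide 80% power".

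**Screening.** Section 9.4.1 quotes about 95% sensitivity and specificity of portable monitoring (PM) against polysomnography (PSG), and expects to screen about 260 patients, shown as 220/0.95. Appendix IV F.3 plans to recruit 240.

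**Endpoints.** The section 8 table lists average 24-hour systolic and diastolic pressure as primary for Aim 1, and central aortic pressure as secondary. Section 9.4.2 sets significance at p < 0.05, compares the groups by two-sample t-test on change, and refers to that table for all variables and analysis goals.

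Elsewhere the hierarchy differs. A primary objective in the synopsis concerns "treatment in reducing central aortic blood pressure (CABP) in AA vs. other (race) veterans", and section 9.4.1 opens: "The primary goal of this initial study is to estimate differences in the effect size of AUTOPAP treatment on ABP and CABP". Sleepiness is a primary objective in the synopsis ("To test daytime dysfunction (excessive daytime sleepiness; EDS) as a moderator of reduction in ABP and CABP") but appears under secondary objectives in section 2.2 ("Thus, we will examine EDS as a moderator of hypertension response to AUTOPAP treatment").

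**The concern.** The step from 10-20% attrition to 220 enrolled is valid only at 10%. The synopsis presents 12.5% as reassuring because it is below 20%, but the calculation never used 20%, and 12.5% is above the 10% it did use.

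The stated 80% also applies to one endpoint at one threshold. With two primaries and no rule, a reader cannot tell which result decides the study. If one significant result is enough, the overall false-positive rate exceeds 5%. If both are needed, power is below 80% at the planning effect.

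Finally, the screening division is wrong, and its divisor measures something other than the share of screened patients who qualify.

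**Working it through.** **Inputs.** Two-sided alpha 0.05, d = 0.40, 99 per group, attrition 10-20%, 220 enrolled, pilot effects 0.42 and 0.53, PM accuracy 0.95 (all section 9.4.1); 110 per group and dropout 2/16 (synopsis); two primaries (section 8). The correlation between the systolic and diastolic test statistics is not given; 0 to 0.9 is assumed.

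**1. The plan's own figures.** Two-sample t-test, noncentrality = d × √(n/2) with n per group.
- Required n for d = 0.40 at 80% power: 99.08 per group.
- At n = 99: noncentrality 0.40 × √49.5 = 2.81, power 0.7997.
- 198/0.90 = 220.

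So 198 and 220 both reproduce at 10% attrition.

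**2. Power across the stated attrition range, 220 enrolled, per endpoint.**

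| Attrition | Completers | d = 0.40 | d = 0.42 | d = 0.53 | Detectable d at 80% |
|---|---|---|---|---|---|
| 10% | 220 × 0.90 = 198 | 0.80 | 0.84 | 0.96 | 0.400 |
| 12.5% | 220 × 0.875 = 192.5 | 0.79 | 0.83 | 0.96 | 0.406 |
| 20% | 220 × 0.80 = 176 | 0.75 | 0.79 | 0.94 | 0.425 |

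The exact 95% interval for 2/16 is 2% to 38%, so the observed rate does not settle where in the range attrition will fall.

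**3. Two primaries.** Bivariate normal test statistics, with t critical values for power.
- *Either suffices, each at 0.05.* Under independence, familywise error is 1 − 0.95² = 9.75%. It falls to 7.8% at correlation 0.8 and 7.0% at 0.9.
- *Both required, d = 0.40 on each.* With 198 completers, power is 0.64 (correlation 0), 0.73 (0.8) and 0.75 (0.9). With 176 it is 0.57, 0.67 and 0.70.
- *Both required at the pilot effects 0.42 and 0.53.* Power is 0.80 to 0.84 with 198 completers and 0.74 to 0.79 with 176.
- *Holm at overall 0.05, power for each endpoint, d = 0.40.* 0.75 to 0.78 with 198 and 0.70 to 0.72 with 176.

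**4. Screening.** 220/0.95 = 231.6, so 232. The stated 260 implies that 220/260 = 85% of those screened qualify. The divisor is also the wrong quantity. PSG has been dropped and PM AHI ≥ 15/hour is itself the entry criterion, so the relevant figure is the share of screened patients who meet it. The documents do not give that share.

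**5. The 240 in Appendix IV F.3.** If 240 started treatment, 198 completers would be 198/240 = 82.5%, allowing 17.5% attrition. With 220 the allowance is 10%. The two targets are different plans.

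**The case against.** The attrition loss is 1 point at 12.5% and 5 points at 20%. The planning effect of 0.40 is already below both pilot effects; at d = 0.42, 220 enrolled keep 80% power up to about 18% attrition. This stands and limits the weight of the point, though the pilot effects are for office pressure, not the 24-hour pressure to be tested.

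The synopsis names no effect size, so its 80% could be read at 0.42. That is hard to sustain, because it rests on the plan's own sample size calculation, which uses 0.40. Section 7.3 promises continued follow-up after withdrawal for adverse experience, and section 9.4.2 allows multiple imputation. Both soften the loss, but the primary t-test as written uses only patients with both measurements.

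On multiplicity, the study calls itself initial, frames its goal as estimation, and compares race groups rather than randomised arms. No passage says that either primary suffices or that both are required, so the figures in step 3 are conditional. This stands. But the same section powers a two-tailed 0.05 test, and the synopsis states a directional hypothesis, so a rule is still needed. The hierarchy conflict is partly answered, since section 9.4.2 points to the section 8 table.

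Three stronger readings are tempting and not supported:
- **That 260 comes from a 20% attrition calculation.** (198/0.80)/0.95 = 260.5 fits, but the documents do not say so.
- **That the investigator's regular data checks (section 9.3) mean between-group results have been seen.** They are described as quality control.
- **That PVT lapses, primary for Aim 2, must be demoted.** Their study-level status is for the sponsor to state.

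**Conclusion.** The point holds, with unequal weight across its parts. The attrition and screening statements are wrong as written but minor: at d = 0.40 the loss is 1 to 5 points of power within the plan's own range, and the screening error affects recruitment planning only. A reader might infer that the study is seriously underpowered. The documents do not support that, since power at 20% attrition is 0.79 and 0.94 at the pilot effects.

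The missing rule for systolic and diastolic pressure matters more and should be fixed. The stated 80% is per endpoint. It does not describe the power of a both-required rule at d = 0.40 (about 64-75% with 198 completers), and an either-suffices rule at 0.05 each would carry about 7-10% familywise error. These sizes rest on an assumed correlation of 0 to 0.9 and on a rule that the sponsor has not yet chosen.

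**What to change.** Keep n = 220.

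**(a) Power statement (section 9.4.1 and synopsis).** Suggested text: *With 220 enrolled, a two-sample t-test at two-sided 0.05 has per-endpoint power for d = 0.40 of 80% at 10% attrition (198 completers), 79% at 12.5% and 75% at 20% (176 completers; detectable d 0.425).* Delete the suggestion that dropout below 20% supports 80% power.

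**(b) Success rule.** In a dated amendment that says whether any between-group result has been seen, test systolic and diastolic pressure with Holm at overall 0.05. This keeps both primaries of section 8. Power for each endpoint at d = 0.40 is about 75-78% at 10% attrition and 70-72% at 20%; give the assumed correlation. If the sponsor prefers both required, or a single primary, state the power that matches (step 3, or the table in step 2). Align the synopsis objectives, sections 2.1 and 2.2 and the first sentence of 9.4.1 with the section 8 table, and have the sponsor state the study-level status of PVT lapses.

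**(c) Screening and recruitment.** Correct 220/0.95 to 232, or better, use the site's own share of screened patients with PM AHI ≥ 15/hour and state it. Reconcile the result, and the 220, with the 240 in Appendix IV F.3.

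**Cost.** One amendment, with no added patients or procedures. The stated power becomes slightly less favourable. Because the study is already running, a rule set now can look data-driven, hence the date and the disclosure.

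### The sleepiness objective has no designated blood pressure test: the Aim 2 primary test uses no BP data, and at least 16 sleepiness–BP tests are each read at p<0.05

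*Combined protocol and SAP*

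**What the plan says.** **Objective.** Primary Objective 4 in the synopsis reads "To test daytime dysfunction (excessive daytime sleepiness; EDS) as a moderator of reduction in ABP and CABP". Section 2.2 puts the same question under secondary objectives.

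**Outcomes table (Section 8).** The one Aim 2 item labelled primary is a between-group comparison: "change in number of PVT lapses". The items that link sleepiness to the Aim 1 outcomes are labelled secondary and within-group. They are change in PVT lapses with the Aim 1 primary outcome, change in PVT lapses with the Aim 1 secondary outcomes, and "Association of change in ESS scores with outcomes of specific aim 1".

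**Analysis (Section 9.4.2).** The Aim 2 primary outcome gets a two-sample t-test. For the rest: "Secondary outcomes will be assessed with partial correlations implemented with PROC CORR in SAS". One threshold covers everything: "A p-value < 0.05 will be considered significant". A later paragraph on moderators describes adding Z and a Z*X interaction to a linear model. Its example of Z is gender; sleepiness is not mentioned.

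**Synopsis, sleepiness as moderators.** Both baseline ESS/PVT and change in ESS/PVT are to be tested against effectiveness endpoints 1 to 3.

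No hierarchy, designated sleepiness–BP test or multiplicity procedure appears in Section 8 or Section 9.4.

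**The concern.** The Aim 2 primary test takes PVT change and race as inputs. Blood pressure does not enter it, so whatever it shows, it says nothing about whether sleepiness bears on the BP response. Objective 4 must therefore be answered by something else, and the plan offers three candidates without choosing: change-on-change correlations, baseline associations, and an interaction model that is never connected to sleepiness. Each would be called significant at 0.05.

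If the choice is left until the data are seen, one nominally significant association can be reported as support for Objective 4 even when none exists, and a reader could not tell how many other tests were available.

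**Working it through.** **1. The plan's own figure.** Section 9.4.1 states that "99 patients in each group (total n = 198) will provide power of 0.8". The inputs given there are a standardised between-group difference of 0.4 and two-sided testing at 0.05. By normal approximation, n = 2(1.960 + 0.842)² / 0.4² = 98.1, rounded up to 99 per group. The t-based solution is 99.08, with power 0.7997 at 99. The figure reproduces, and 198/0.90 = 220. It is a calculation for one between-group comparison and makes no provision for the Aim 2 associations.

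**2. Counting the Aim 2 associations from the Section 8 table.**
- BP outcomes: 24-hour SBP, 24-hour DBP, central aortic BP (counted once), 24-hour mean BP = 4.
- Urine outcomes: norepinephrine, normetanephrine, 8-isoprostane = 3.
- Sleepiness changes: PVT lapses, ESS = 2. Groups: 2.
- BP only: 4 × 2 × 2 = **16**. All outcomes: 7 × 2 × 2 = **28**, of which 12 are urine biomarkers.

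Splitting central BP into systolic and diastolic would give 20 and 32. Running the synopsis's baseline associations within group as well would double 16 to 32 and 28 to 56.

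**3. Chance of at least one p<0.05 with no true association.** If the tests were independent:
- 16 tests: 1 − 0.95¹⁶ = 0.560
- 28 tests: 1 − 0.95²⁸ = 0.762, with 28 × 0.05 = 1.4 false positives expected.

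The outcomes are correlated, and the documents give no correlations, so the values below are **assumptions**. Each row is 10,000 simulated trials with 99 patients per group and two-sided 0.05. Mean BP is computed from SBP and DBP, taking the SD of SBP change as 1.4 times that of DBP change.

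| SBP–DBP and SBP–central BP | NE–NMN | BP–catecholamine / with 8-isoprostane | PVT–ESS | Any of 16 BP tests | Any of 28 |
|---|---|---|---|---|---|
| 0 | 0 | 0 / 0 | 0 | 49% | 73% |
| 0.4 | 0.3 | 0.1 / 0.1 | 0.1 | 45% | 70% |
| 0.6 | 0.5 | 0.2 / 0.1 | 0.2 | 40% | 66% |
| 0.7 | 0.6 | 0.2 / 0.2 | 0.3 | 38% | 63% |
| 0.8 | 0.7 | 0.3 / 0.3 | 0.4 | 34% | 58% |
| 0.85 | 0.8 | 0.4 / 0.4 | 0.6 | 31% | 53% |

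(NE = norepinephrine, NMN = normetanephrine. DBP–central BP was set at 0.8 times SBP–central BP.)

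The plan specifies partial correlations. The Section 8 covariates use about 17 degrees of freedom: 10 socio-demographic (income, with five levels, takes 4), 2 for OSA severity, 2 for comorbidity and 3 treatment-related. Removing 17 df moved each figure by at most about 1.5 percentage points.

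**4. Price of control.** By Fisher z, power = Φ(atanh(r)·√(n − k − 3) − z₁₋α/₂), with r = 0.30, atanh(r) = 0.3095, n = 99 and k covariate df. The level 0.0125 is the strictest Holm step for four tests (0.05/4).

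| k | atanh(r)·√(n − k − 3) | Power at 0.05 | Power at 0.0125 |
|---|---|---|---|
| 0 | 0.3095 × √96 = 3.03 | 86% | 70% |
| 17 | 0.3095 × √79 = 2.75 | 79% | 60% |

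**The case against.** **Moderation has its own model.** Section 9.4.2 says the interaction coefficient tests a moderator effect, so Objective 4 need not depend on the correlations. This stands in part: a reader might infer that the objective rests wholly on 28 correlations, and the documents do not support that. But the paragraph is generic. It names neither sleepiness as Z, nor X, nor the BP outcome, and does not say it replaces the correlations. Unless tied down, it is one more candidate test.

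**These are secondary associations in an initial study.** The table labels them secondary, Section 2.2 does the same for the objective, and Section 9.4.1 speaks of estimating effects. Unadjusted secondary results are common in such work. This lowers the seriousness but does not remove the point, because the synopsis still calls the objective primary and the same significance threshold applies.

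**An order is implied.** PVT change with the Aim 1 primary outcome is listed first. A list is not a testing order, and that item alone is four tests (SBP and DBP in two groups).

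**The 28-test rate is the wrong family.** This is correct for Objective 4, which concerns ambulatory and central pressure. The 12 biomarker tests lie outside it, and the relevant family from the table is the 16.

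**Conclusion.** The point holds. No test linking sleepiness to blood pressure is designated for an objective the synopsis calls primary, the test labelled primary cannot answer it, and the available tests carry no multiplicity control.

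Under the null, the chance of at least one nominally significant result is about 31–56% for the 16 BP correlations, and about 53–76% for all 28. The upper ends assume independence; the rest depends on correlations that the documents do not supply. The figures also measure the event that any one test is significant. No section says that a single significant result would count as success.

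A reader might go further and infer that a null trial would more often than not yield a false sleepiness–BP finding. The Section 8 table does not support that: in every simulated scenario the 16-test rate is below one half, and it passes one half only if the tests are close to independent. The rate exceeds one half throughout only when the urine biomarkers are counted. The Aim 1 between-group BP comparison is not affected.

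**What to change.** Reconcile the synopsis (Objective 4 and the sleepiness items), Section 2.2, the Section 8 table and Section 9.4.2 on the status of the sleepiness objective and on how it is tested. Then, before analysis:

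1. Name one small sleepiness–BP set as the only basis for the Objective 4 conclusion. The better choice is the Section 9.4.2 moderator model with baseline PVT lapses as Z and 24-hour SBP and DBP as outcomes, plus central aortic BP if Objective 4 keeps it. A correlation between two changes over the same three months is not a test of moderation.
2. State what X is. All patients receive AUTOPAP, so with X as time (before/after) the interaction is the association of baseline PVT lapses with BP change. With X as race, it asks a different question.
3. Apply Holm within that set at an overall 0.05, and say whether the groups are combined (two tests, or three with central BP) or separate (four, or six).
4. Report the change-on-change correlations, ESS results and urine biomarker associations as estimates with 95% CIs and no significance claim.
5. Keep the comparison of PVT change by race, and state that it does not test Objective 4.

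This changes wording only and needs no new data. The cost is lower power per test, as shown in step 4 of the working for four tests at n=99, and the remaining associations become supportive only.
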